5.2 Missing Data

The pattern of missing data will be described for the secondary and tertiary outcomes. Differences in subject characteristics (demographics, BMI) and outcomes by whether or not the subject started the intervention or completed the study will be examined.

5.3 Thematic Content Analysis (Aim 1)

Interviews will be audiotaped and transcribed through a professional transcription service. Transcribed data will be coded by two trained coders using thematic content analysis with a constant comparison approach in a qualitative analysis software program (NVivo Version 12.5, QSR International, 2019).¹² Coders will read each transcript independently. Repeated ideas and important quotes will be identified and used to develop an initial codebook, an organized list of codes and memos. During a second reading of interview transcripts, each interview will be compared and contrasted with the initial codebook. Revisions will be made, and the codebook

will be updated. Through an iterative process, coders will meet to compare codebooks and will revise or reject codes as needed. If disagreements between coders cannot be resolved, a roundtable consisting of co-investigators will be convened to resolve disagreements and make final decisions on codes. All codes will be organized into groups of related concepts that will inform emergent themes.¹³ A final reading will determine if all themes are saturated and that there are no additional themes identified. Two key strategies will be used to enhance the rigor and accuracy of the qualitative analysis, we will: (1) use active discourse with respect to coding, organization of coding categories, and identification of emerging themes, and (2) consult with [name] (Co-Investigator), who is a highly trained qualitative researcher who will review all themes and associated quotes, and make suggestions for coding modifications.¹⁴

5.4 Main Analyses of Secondary and Tertiary Outcomes (Aim 2)

Since this is a feasibility study, quantitative assessment of the outcomes will be considered preliminary. The objective of these preliminary analyses is to demonstrate whether the intervention shows promise in changing the PA, SB, and sleep behaviors. Emphasis will be placed on describing the variability in the outcomes using measures of central tendency including mean, standard deviation, and 95% confidence intervals.

Comparisons of continuous variables between treatment groups will be conducted using t-tests or a non-parametric analogue (Mann-Whitney U test). Comparisons within treatment group will be tested using paired t-tests or the signed rank test. Comparisons of categorical variables between groups will be assessed using Chi-square or Fisher's exact tests; McNemar test will be used within groups. The reliability of the psychological needs and autonomous motivation scales will be assessed using Cronbach's alpha. Examination of clinically meaningful effects,¹⁵ and estimation of the reliable change index¹⁶ will be conducted.

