**Analyses of Secondary and Tertiary Outcomes:** Comparisons of PA, SB, sleep, BMI, waist circumference, blood pressure, and heart rate between (Mann-Whitney U test) and within treatment groups (pre to post; paired t-tests, signed rank test) will be tested. Cronbach's alpha will be used to assess the reliability of the psychological needs satisfaction and autonomous motivation for PA scales. While clinically significant changes in secondary and tertiary outcomes are not

expected, we will examine clinically meaningful effects and estimate the reliable change index. These analyses will guide power calculations for future trials.

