3.4 Tertiary Outcomes (Aim 2)

Percentage over the 95th percentile in body mass index (BMI)

Psychological needs (Psychological Need Satisfaction in Exercise Scale), and autonomous motivation (Behavioural Regulation in Exercise Questionnaire-2).

4 Study Design

To address the research question, "**Is a technology-based intervention that promotes PA, SB, and sleep, feasible among Hispanic adolescents with obesity?**" a two-armed, pre-post design will be used to test the feasibility of the intervention compared to a wait-list control group. Limitations of previous studies include the absence of control groups.^{6,7} A wait-list control comparison is appropriate for studies in the pre-efficacy phase that aim to assess feasibility.⁸ Another limitation of previous studies is the use of self-reported measures to assess health behaviors.⁹⁻¹¹ We will rely solely on research grade accelerometers to objectively measure wake time and sleep behaviors at baseline (T0) and 12- weeks post-intervention. Following baseline assessments, youth will be randomized in a 1:1 ratio to the intervention or wait-list control using a computerized random number generator in SAS version 9.4 (SAS Institute, INC., Cary, NC). After the 12-week study period, youth in the wait-list control group will be invited to participate in the intervention. A subsample of youth (N=15) initially randomized to the intervention will be invited to participate in an exit in-depth interview.

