5.5 Exploratory Analyses of Secondary and Tertiary Outcomes (Aim 2)

Subgroup analyses by gender will be conducted as exploratory using summary statistics since the study is not power to detect an effect by gender.

A repeated measures model will be used to examine change in PA, SB and sleep. Each outcome will be tested in a separate model. The model will include time, treatment group, and the time by treatment group interaction. The magnitude and direction of the associations using parameter estimates and associated confidence intervals. Potential covariates include subject age, gender and BMI.

Compositional data analysis will be conducted for the PA, SB, and sleep behaviors. After log transformation, the geometric mean of each behaviour and all behaviors together (overall) will be calculated. The log-ratio of each behaviour will be derived by dividing the geometric mean of each behavior by the overall geometric mean. Differences by treatment group will be assessed using t-test. Variability of each behaviour in relation to the other behaviors and variance of the whole composition will be described using a variation matrix. The association of treatment group with the behaviors will be examined using multivariate regression (all outcomes as dependent variables in one model), after adjusting for gender.

References

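### The main between-arm analysis of the continuous secondary and tertiary outcomes ignores the collected baseline and does not say whether it compares 12-week values or changes

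*SAP*

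**What the plan says.** SAP 5.4, the main analysis section for secondary and tertiary outcomes, states: "Comparisons of continuous variables between treatment groups will be conducted using t-tests or a non-parametric analogue (Mann-Whitney U test". It names no covariate and no scale. Protocol G2 names the Mann-Whitney test alone for the between-arm comparison and ties the pre-to-post wording to the within-arm tests: "between (Mann-Whitney U test) and within treatment groups (pre to post; paired t-tests, signed rank test) will be tested".

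Baseline values are part of the design. SAP 4 plans to "objectively measure wake time and sleep behaviors at baseline (T0) and 12- weeks post-intervention", and SAP 3.2 aims for baseline data on every participant.

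The documents give these analyses two uses. SAP 5.4 says "The objective of these preliminary analyses is to demonstrate whether the intervention shows promise in changing the PA, SB, and sleep behaviors", with emphasis on means, SDs and 95% confidence intervals. Protocol G2 adds: "These analyses will guide power calculations for future trials".

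SAP 5.5 adds exploratory models. For the behaviours, "A repeated measures model will be used to examine change in PA, SB and sleep", and its terms are listed as follows: "The model will include time, treatment group, and the time by treatment group interaction". Age, gender and BMI are listed only as possible covariates. The compositional analysis relates arm to all behaviours jointly: "behaviors will be examined using multivariate regression (all outcomes as dependent variables in one model), after adjusting for gender". Neither model lists the baseline value of the outcome as a covariate, and neither covers the tertiary outcomes.

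**The concern.** Two things are left open.

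First, the scale. A t-test on 12-week values and a t-test on changes are both valid in a randomized trial. They differ in precision, and with about 20 per arm they can give different point estimates when baselines differ by chance. The plan does not fix in advance which difference is the main estimate.

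Second, precision. Neither unadjusted version makes best use of the baseline unless r is very low or very high. A judgement of promise, and the design of a later trial, would then rest on intervals wider than the collected data allow. This is a missed improvement and an unstated detail. It does not bias the comparison.

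**Working it through.** **Inputs from the documents.** 48 adolescents randomized 1:1 (Protocol G1, SAP 4); 85% follow-up (SAP 3.2); two-sided 5% tests and 95% intervals (SAP 5.1). Hence 0.85 × 48 = 40.8 analysed, so n = 20.4 per arm and N = 40.8. The plan states no power, effect size or SD for these outcomes, so it has no figure to reproduce.

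**Assumptions.** The outcome has the same SD at both visits, and results are in SD units. The correlation r is not in the documents; I used 0.3, 0.5 and 0.7 and then looked for the break-even points.

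**Formulas.** Variance of the between-arm difference, in units of 2·SD²/n:

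- 12-week value: 1
- change: 2(1 − r)
- ANCOVA: (1 − r²)(1 + 1/(N − 4)), the last factor being the expected cost of chance baseline imbalance

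The 95% half-width is t × √(2/n × factor), with N − 2 degrees of freedom (N − 3 for ANCOVA). Here √(2/20.4) = 0.3131, t = 2.023 (2.025 for ANCOVA), and 1 + 1/36.8 = 1.027.

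For example, at r = 0.5 the ANCOVA factor is 0.75 × 1.027 = 0.770, so the half-width is 2.025 × 0.3131 × √0.770 = 0.556 SD. On 12-week values it is 2.023 × 0.3131 = 0.633 SD.

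| r | 12-week value | Change | ANCOVA | ANCOVA vs 12-week | ANCOVA vs change |
|---|---|---|---|---|---|
| 0.3 | 0.633 | 0.749 | 0.613 | −3% | −18% |
| 0.5 | 0.633 | 0.633 | 0.556 | −12% | −12% |
| 0.7 | 0.633 | 0.491 | 0.459 | −28% | −6% |

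**Detectable difference at 80% power** (noncentral t), in SD:

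| r | 12-week value | Change | ANCOVA |
|---|---|---|---|
| 0.3 | 0.90 | 1.06 | 0.87 |
| 0.5 | 0.90 | 0.90 | 0.79 |
| 0.7 | 0.90 | 0.70 | 0.65 |

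**Where adjustment stops paying.** ANCOVA matches the 12-week comparison at r = 0.168 and the change comparison at r = 0.944. Outside that range it loses at most about 1.4% in width; at r = 0 the loss is 1.43%.

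**Using the database count.** Protocol F2 reports 43 participants. If 85% of these were followed (an assumption), n = 0.85 × 43 / 2 = 18.3 per arm. The detectable differences become 0.95 SD on 12-week values; 1.13, 0.95 and 0.74 on change; and 0.92, 0.84 and 0.69 with ANCOVA. The break-evens are r = 0.179 and 0.936, and the largest loss is 1.6%.

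**Simulation check.** In 40,000 null trials at 20 per arm, mean half-widths were 0.636 on 12-week values; 0.752, 0.636 and 0.493 on change; and 0.615, 0.559 and 0.461 with ANCOVA. All three tests rejected in 4.8% to 5.1% of trials.

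**Does the exploratory repeated-measures model already do this?** With two visits, complete data and unconstrained baseline means, its time-by-group term is the difference in mean change. On one simulated complete data set of 20 per arm, both came to 0.1290 (SE 0.2996). It therefore gives change-score precision.

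**The case against.** The strongest case against is one of weight. Feasibility is primary, no feasibility criterion uses a between-arm result, the SAP calls these results preliminary, and Protocol G2 does not expect clinically significant changes. All of that stands. It limits the importance of the point without removing it, because the documents still assign these analyses the two uses described above.

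The gain also depends on an unknown r. Against whichever unadjusted scale is better, it is 3%, 12% and 6% at r = 0.3, 0.5 and 0.7, falling to about 4% at 0.8 and 1% at 0.9. That is fair. An outcome that tracks very closely over 12 weeks gains little over a change score. But the plan has not committed to the better scale.

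The widths apply to the t-test option, since Mann-Whitney itself gives no interval for a mean difference. This is correct, and it is a further reason to name a main estimate that comes with one.

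With missing follow-up, a likelihood-based repeated-measures model that keeps baseline-only participants would be slightly narrower than the change score. ANCOVA's remaining advantage would then be about 16%, 10% and 5%. The SAP does not say how the model is fitted.

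Complete-case ANCOVA loses anyone without valid baseline accelerometry, and the protocol's wear rule makes that possible. At r = 0.3, losing about 6% of analysed participants cancels the gain over 12-week values; at r = 0.5 it takes about 21%. A model with baseline means constrained equal across arms avoids this loss.

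For power calculations, a later trial needs SDs and r more than it needs a narrow pilot interval. This stands too, and no passage plans to report r.

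**Conclusion.** The point holds as a recommended improvement. The planned test is valid, but its scale is unstated and it leaves precision unused. At about 20 per arm and r between 0.3 and 0.7, baseline adjustment narrows the interval by 3% to 28% against 12-week values and by 6% to 18% against change. For r between about 0.17 and 0.94 it beats both; outside that range it costs at most about 1.4% in width. These figures assume equal SDs at the two visits, 85% follow-up of 48, valid baselines for those analysed, and the t-test rather than the rank test. The exploratory models do not close the gap.

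**What to change.** In SAP 5.4, make the main between-arm estimate for each continuous secondary and tertiary outcome the baseline-adjusted difference at 12 weeks with its 95% confidence interval. Use either ANCOVA or the SAP 5.5 repeated-measures model with baseline means constrained equal across arms and extended to the tertiary outcomes. The constrained model is preferable if some baseline accelerometry is invalid.

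- If the normality checks in SAP 5.1 call for it, transform both time points or give a bootstrap interval.
- Keep the t-test or Mann-Whitney test as a sensitivity analysis, stating whether it uses 12-week values or changes.
- Base statements about promise on the between-arm estimate and present within-arm change descriptively.
- Report the SDs and the baseline to 12-week correlation for each outcome.
- Bring Protocol G2 into line with the SAP.

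The cost is one or two degrees of freedom and a dated amendment to both documents, with no new data. Protocol F2 says data collection has concluded, so the change should be labelled post hoc if outcomes by arm have been seen, with the planned tests reported alongside.

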5.5 Exploratory Analyses of Secondary and Tertiary Outcomes (Aim 2)

Subgroup analyses by gender will be conducted as exploratory using summary statistics since the study is not power to detect an effect by gender.

A repeated measures model will be used to examine change in PA, SB and sleep. Each outcome will be tested in a separate model. The model will include time, treatment group, and the time by treatment group interaction. The magnitude and direction of the associations using parameter estimates and associated confidence intervals. Potential covariates include subject age, gender and BMI.

Compositional data analysis will be conducted for the PA, SB, and sleep behaviors. After log transformation, the geometric mean of each behaviour and all behaviors together (overall) will be calculated. The log-ratio of each behaviour will be derived by dividing the geometric mean of each behavior by the overall geometric mean. Differences by treatment group will be assessed using t-test. Variability of each behaviour in relation to the other behaviors and variance of the whole composition will be described using a variation matrix. The association of treatment group with the behaviors will be examined using multivariate regression (all outcomes as dependent variables in one model), after adjusting for gender.

References

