**Assessments Primary Outcomes:** Feasibility will be evaluated using a priori criteria: recruitment, data collection, the integrity of the study protocol, technical issues, internal consistency of measures, and satisfaction. Given this study's high potential for dissemination in clinical settings, 'Recruitment' and 'Data Collection' criteria will assess the feasibility of recruiting and retaining participants from community clinics. 'Integrity of Study Protocol' criteria will be used to identify the feasible and acceptable 'dose' of the intervention. 'Technical Issues' criteria will assess the feasibility of using the Fitbit device and text messaging as behavior change tools. 'Internal Consistency of Measures' criteria will assess the appropriateness of our instruments for Hispanic youth. 'Satisfaction' will assess acceptability, which is especially important for interventions in minority populations. This will provide information on the availability of high-risk youth in community clinics and the ability of our recruitment strategies to engage youth from these settings.

**Secondary outcomes:** Physical activity, sedentary behaviors, and sleep will be assessed using a hip-worn wGT3X-BT accelerometer (Actigraph, Pensacola, Florida). Participants will wear the accelerometer 24 hours a day for 7 days at both timepoints. A research team member will review instructions for device wear and will send daily text messages to remind participants to wear the device to promote compliance. Accelerometer data will be processed using ActiLife v6.13 software. A valid day of wear will be defined as  $\geq 18$  hours of wear on 4 days or more, one of which has to be a weekend day. Evenson cut points will be used to analyze and categorize SB (defined as <100 counts per minute) and moderate-to-vigorous PA. The Sadeh algorithm will be used to assess sleep duration. While wrist-worn devices are superior for assessing all sleep characteristics (i.e. sleep efficiency, wake after sleep onset, etc), hip-worn devices provide accurate measures of sleep duration and timing. Participants will be asked to complete a wear log to indicate wake and sleep times, which will be used to verify accelerometer data. Data will be reported as average minutes per day spent in PA, SB, and sleep.

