**Exit-Interviews.** A subsample of participants (N=15) randomized to the intervention will participate in a 1-hour, post-intervention exit interview

Data collection for this study has been concluded. The current database includes N=43 participants. To conduct further analysis and maximize the potential knowledge to be gained from this study we will collaborate with students and faculty at Rice University through the Data 2 Knowledge capstone program to conduct high-level analysis to identify patterns of 24-hour physical activity and sleep behaviors and their associations with metabolic health. Data shared through this capstone program will be de-identified and will include demographic information, accelerometer derived physical activity, sleep, and sedentary behaviors, anthropometrics (BMI, height, weight, waist circumference), zipcode (not full address) as well as surveys on autonomous motivation. An IRB protocol will be submitted at Rice University and all faculty and students working on this project will be added to the IRB protocol at Rice University.

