3.2 Primary outcome (Aim 2)

Feasibility is the primary outcome and will be evaluated for the development of a larger trial using the following a priori feasibility criteria:^{1,2}

1. **Recruitment:** Recruit and enroll 48 Hispanic adolescents 14-16 years of age with obesity from community clinic settings.
2. **Data Collection:** Collect data on 100% of participants at baseline and 85% of participants at post-intervention.
3. **Integrity of Study Protocol:** Participants wear their Fitbit device for ≥ 5 days/week and respond to 80% of text messages when prompted throughout the 12-week intervention.
4. **Internal Consistency of Measures:** Cronbach's alpha for survey scales ≥ 0.7 .
5. **Technical Issues:** $\leq 10\%$ technical issues with the transmission and receipt of text messages or Fitbit device functioning.
6. **Satisfaction:** $\geq 80\%$ report 'excellent' – 'good' satisfaction with the intervention.

'Recruitment' and 'Data Collection' criteria will assess the feasibility of recruiting and retaining participants from community clinics.³ We will record the number of participants that are screened, enrolled, and the time and resources that it takes to complete recruitment activities and reach our recruitment goal (N=48). This data will provide information on the availability of eligible, high-risk youth in partnering clinics and the ability for our recruitment strategies to engage youth from these

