3.3 Secondary Outcomes (Aim 2)

Physical activity (PA), sedentary behaviors (SB), and sleep (min/day) will be measured in min/day.

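### SAP 5.5's exploratory compositional regression adjusts for gender only and states no use of the baseline composition, which could narrow the treatment-effect interval at little cost

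*SAP*

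**What the plan says.** The compositional paragraph of SAP 5.5 ends with one sentence on a regression of the behaviours on treatment group, to be "examined using multivariate regression (all outcomes as dependent variables in one model), after adjusting for gender". Gender is the only covariate named. The sentence mentions no baseline value, change score, time term or visit.

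The scale is also left open. Earlier in the paragraph the SAP defines a log-ratio: "The log-ratio of each behaviour will be derived by dividing the geometric mean of each behavior by the overall geometric mean". The regression sentence does not refer back to it, and SAP 3.3 defines the outcomes in minutes: "Physical activity (PA), sedentary behaviors (SB), and sleep (min/day) will be measured in min/day".

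Baseline data are collected by design. SAP 4 (Study Design) relies on accelerometers to "objectively measure wake time and sleep behaviors at baseline (T0) and 12- weeks post-intervention", and Protocol F2 says: "Participants will wear the accelerometer 24 hours a day for 7 days at both timepoints".

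The repeated measures models in SAP 5.5 include time, arm and their interaction, with a separate model for each outcome. Protocol G2 does not mention a compositional analysis.

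**The concern.** In a small randomised study, a participant's own baseline value is usually the covariate most worth adjusting for. Here it is measured with the same device and wear protocol as the outcome. Gender is adjusted for, yet no use of the baseline composition is stated. If the regression is run at 12 weeks as worded, the arm estimate carries between-participant variation that the baseline recording could partly explain.

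What is at stake is the width of the interval for arm. SAP 5.4 describes the outcome analyses as preliminary and says "Emphasis will be placed on describing the variability in the outcomes", using 95% confidence intervals among other summaries. Protocol G2 says the secondary and tertiary analyses will guide power calculations for later trials. Neither statement sets a precision target for this model, but both make a tighter interval worth having.

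**Working it through.** The plan gives no figure to reproduce: Protocol G1 says no formal power calculation was used, and neither document gives a standard deviation or a correlation for these outcomes.

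**Inputs**
- Stated model terms: arm and gender (SAP 5.5). Intervals are two-sided 95% (SAP 5.1).
- Sample: 48 planned. SAP 3.2 sets the target "Collect data on 100% of participants at baseline and 85% of participants at post-intervention", and 0.85 × 48 = 40.8, about 41. Protocol F2 says: "Data collection for this study has been concluded. The current database includes N=43 participants". The number with valid recordings at both visits is not given, so 41 and 43 are used as working values.
- Correlation ρ between a coordinate at baseline and at 12 weeks: assumed 0, 0.3, 0.5 and 0.7.
- Simulation: assumed geometric centres for PA/SB/sleep of 240/690/510 min, log SDs of 0.30/0.15/0.12, and 3,000 runs per cell.

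**Step 1. Gain before the cost of extra terms.** If each coordinate correlates ρ with its own baseline and the other baseline coordinate adds nothing, the residual SD is multiplied by √(1 − ρ²). This is 0.954, 0.866 and 0.714 at ρ = 0.3, 0.5 and 0.7.

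**Step 2. Cost.** Two added terms take the residual degrees of freedom at n = 43 from 43 − 3 = 40 to 38. At ρ = 0, where only the cost is visible, the simulated ratio of mean interval widths (adjusted over unadjusted) is 1.027 at n = 43 and 1.030 at n = 41.

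**Step 3. Net ratio of interval widths**

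| ρ | 1.027 × √(1 − ρ²) | simulated, n = 43 | simulated, n = 41 |
|---|---|---|---|
| 0 | 1.027 | 1.027 | 1.030 |
| 0.3 | 0.980 | 0.978 | 0.982 |
| 0.5 | 0.889 | 0.893 | 0.890 |
| 0.7 | 0.733 | 0.734 | 0.734 |

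The interval is therefore about 2%, 11% and 27% narrower at ρ = 0.3, 0.5 and 0.7, and about 3% wider at zero. The formula contains neither the assumed centres nor the spreads.

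**Step 4. Break-even.** Setting 1.027² × (1 − ρ²) = 1 gives ρ² = 1 − 1/1.0547 = 0.052, so ρ is about 0.23. Simulation (6,000 runs, n = 43) gave 1.003 at 0.22 and 0.998 at 0.24.

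**Step 5. Missing baselines.** Protocol F2 requires at least 18 hours of wear on at least 4 days, one of them at a weekend, so some participants may lack a valid baseline recording. The ratios below are relative to the unadjusted interval on all 43, with baselines missing at random.

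| Handling | ρ = 0.3 | ρ = 0.5 | ρ = 0.7 |
|---|---|---|---|
| 2 dropped | 1.007 | 0.916 | 0.756 |
| 4 dropped | 1.04 | 0.94 | 0.78 |
| 8 dropped | 1.11 | 1.00 | 0.83 |
| 4 kept, pooled mean filled in | 0.985 | 0.902 | 0.769 |
| 8 kept, pooled mean filled in | 0.990 | 0.917 | 0.800 |

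With filling in, coverage of the 95% intervals was 94.3% to 96.0%.

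**Step 6. Scale.** Three centred log-ratios computed per participant sum to zero, so their residual covariance matrix has rank 2 of 3 and a three-variate joint test cannot be formed. Two log-ratio coordinates give rank 2 of 2. Unclosed minutes, with daily totals between 18 and 24 hours, give rank 3 of 3.

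**The case against.** The strongest reply is that little depends on this model. It is exploratory, SAP 5.4 calls the outcome analyses preliminary, and none of the six feasibility criteria in SAP 3.2 uses it. Baseline already enters the repeated measures models for each behaviour. The gain rests on a correlation the documents do not give, and below about 0.23 adjustment costs precision. Dropping participants without a valid baseline can remove the gain. Data collection has ended, so choosing covariates now adds post hoc flexibility, which dating the change discloses but does not remove.

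All of this stands and sets the priority. It does not remove the point, because the separate models do not treat the three behaviours as one composition.

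A reader might infer more than the documents support:
- *That no comparison of the whole composition will use baseline.* The visit is not stated, so an analysis of change in log-ratios remains possible. The text supports only that use of baseline is not stated.
- *That the regression as planned cannot be computed.* The singular matrix matters only if all three centred log-ratios are tested jointly. The SAP names no joint test, and neither document closes the minutes to 24 hours.
- *That separate results for each behaviour are sound however the text is read.* This cannot be asserted either. Stacking both visits without a within-participant term would give wrong intervals, and the log-ratio wording could mean group-level geometric means, which leave no participant values to compare.
- *That 43 is the number of complete pairs.* It is a database count.

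**Conclusion.** The point holds as a low-priority improvement in precision. SAP 5.5 names gender and no baseline term for the compositional regression, while the baseline composition is measured under the same procedure. A 12-week comparison by randomised arm without baseline adjustment is unbiased, so no bias is claimed.

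The size runs from about 3% wider at zero correlation to about 27% narrower at 0.7. It assumes 41 to 43 complete pairs, a similar correlation for both coordinates and, where baselines are missing, missingness at random. Confidence is high that baseline use, scale and visit are unstated, and only moderate that log-ratios are the intended dependent variables.

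**What to change.** In SAP 5.5, state that:
1. the dependent variables are two log-ratio coordinates calculated for each participant at 12 weeks (any two centred, or two isometric, log-ratios);
2. the model contains arm, gender and the two matching baseline coordinates;
3. participants without a valid baseline recording stay in the model, for example by filling in the baseline mean pooled over both arms, so that the filled value does not depend on arm;
4. any joint test of arm has 2 degrees of freedom.

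Date the amendment and label it as made after data collection ended. The variation matrix can stay as planned.

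The cost is a few sentences, a few lines of code and two residual degrees of freedom per coordinate. Item 3 is needed to protect the gain: at a correlation of 0.3, dropping 2 of 43 participants already cancels it.
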